10.3. Adverse Event Reporting Guidance for Patient and/or Caregiver Survey Responses

The patient questionnaire for this study will be completed online via a secure website. The online surveys do not include questions that could potentially identify a safety event, nor does it provide a free text field where study participants could specify information that may constitute a safety event. Responses indicative of “bleeding” and / or “pain” reported through the patient completed closed item questionnaire < see ANNEX 2> are considered hemophilia events that are related to the condition of hemophilia, or directly as a consequence of the bleeding event and are not considered as an adverse event and reportable.

REQUIREMENTS

This study does not involve data collection on clinical endpoints on individual patients. There is no mechanism by which information on safety events for an individual patient will be captured by a study participant during the course of data collection; thus reporting of adverse events is not feasible in the data collection process. However, any information on a safety event inadvertently volunteered by a study participant during the course of this research must be reported as described below.

The survey CRF for this study will be completed online via a secure website. The survey does not include questions that could potentially identify a safety event, nor does it provide a free text field where study participants could specify information that may constitute a safety event. Further, routine communication with study participants via email or phone with the Programme staff is not expected during the conduct of the study. However, it is possible that a study participant may provide information that could constitute a safety event (e.g., serious and non-serious AEs and/or scenarios involving exposure during pregnancy, exposure during breast feeding, medication error, overdose, misuse, extravasation, lack of efficacy and occupational exposure) to Programme staff while in conversation about the survey CRF for any other reason (e.g., seeking information about the purpose of the study). In the event that a study participant in the study reports a safety event associated with the use of the Pfizer product, the Programme staff will complete a non-interventional study (NIS) adverse event monitoring (AEM) Report Form and submit to Pfizer within 24 hours of becoming aware of the safety event. Included in the completion of the NIS AEM Report Form is the study participant's contact information as the reporter, as well as the contact information for the applicable primary healthcare provider; complete contact information should be obtained so that, once the NIS AEM Report Form is transferred to Pfizer, the NIS AEM Report Form will be assessed and processed according to Pfizer's standard operating procedures, including requests for follow-up regarding the safety event to the study participant, or as appropriate, the individual patient's primary healthcare provider..

All Programme staff will complete the Pfizer requirements regarding training on the following: "*Your Reporting Responsibilities: Monitoring the Safety, Performance and Quality of Pfizer Products (Multiple Languages)*" and any relevant Your Reporting Responsibilities supplemental training. This training must be completed by the Programme staff prior to the start of data collection. All trainings include a "Confirmation of Training Certificate" (for signature by the trainee) as a record of completion of the training, which must be kept in a retrievable format. Copies of all signed training certificates must be provided to Pfizer.

11. PLANS FOR DISSEMINATING AND COMMUNICATING STUDY RESULTS

Following the conclusion of patient recruitment, Kantar Health will provide Pfizer with a final summary report of the study findings. A summary will be made available to a participant upon request.

For all publications relating to the Study, Pfizer will comply with recognized ethical standards concerning publications and authorship, including Section II - "Ethical Considerations in the Conduct and Reporting of Research" of the Uniform Requirements for Manuscripts Submitted to Biomedical Journals, <http://www.icmje.org/index.html#authorship>, established by the International Committee of Medical Journal Editors.

11.1. Publications by Investigators

Pfizer has no objection to publication by Investigator of any information collected or generated by Investigator, whether or not the results are favorable to the Investigational Drug. However, to ensure against inadvertent disclosure of Confidential Information or

unprotected Inventions, Investigator will provide Pfizer an opportunity to review any proposed publication or other type of disclosure before it is submitted or otherwise disclosed.

Investigator will provide manuscripts, abstracts, or the full text of any other intended disclosure (poster presentation, invited speaker or guest lecturer presentation, etc.) to Pfizer at least 30 days before they are submitted for publication or otherwise disclosed. If any patent action is required to protect intellectual property rights, Investigator agrees to delay the disclosure for a period not to exceed an additional 60 days.

Investigator will, on request, remove any previously undisclosed Confidential Information (other than the Study results themselves) before disclosure.

If the Study is part of a multi-center study, Investigator agrees that the first publication is to be a joint publication covering all centers. However, if a joint manuscript has not been submitted for publication within 12 months of completion or termination of the Study at all participating sites, Investigator is free to publish separately, subject to the other requirements of this Section.

For all publications relating to the Study, Institution will comply with recognized ethical standards concerning publications and authorship, including Section II - "Ethical Considerations in the Conduct and Reporting of Research" of the Uniform Requirements for Manuscripts Submitted to Biomedical Journals, <http://www.icmje.org/index.html#authorship>, established by the International Committee of Medical Journal Editors.

Publication of study results is also provided for in the Clinical Study Agreement between Pfizer and the institution. In this section entitled Publications by Investigators, the defined terms shall have the meanings given to them in the Clinical Study Agreement.

12. COMMUNICATION OF ISSUES

In the event of any prohibition or restriction imposed (e.g., clinical hold) by an applicable Competent Authority in any area of the world, or if the investigator is aware of any new information which might influence the evaluation of the benefits and risks of a Pfizer product, Pfizer should be informed immediately.

In addition, the investigator will inform Pfizer immediately of any urgent safety measures taken by the investigator to protect the study patients against any immediate hazard, and of any serious breaches of this NI study protocol that the investigator becomes aware of.

14. LIST OF TABLES

None

15. LIST OF FIGURES

None

Appendix 1. LIST OF STAND ALONE DOCUMENTS

Number	Document reference number	Date	Title
1	Appendix A	In design	Patient/Caregiver Informed Consent Form
2	Appendix B	In design	Patient/Caregiver Questionnaire
3	Appendix C	In design	Physician CRF

Appendix 2. FACTOR USE BEHAVIOR QUESTIONS

In responding to this question, please think about what ‘you did’ / ‘the child with hemophilia did’ over the past month.

For the factor replacement therapy ‘you use’ / ‘the child with hemophilia uses’ to prevent and control bleeds, over the past month, how many times did ‘you’ / ‘the child with hemophilia had to’ **use an extra infusion for each of the following reasons?**

Felt pain which I thought was a bleed	Never	1 time	2 times	3 times	4 times or more
Bleeding episode	Never	1 time	2 times	3 times	4 times or more
Wanted additional protection before engaging in a sport or other impact activity	Never	1 time	2 times	3 times	4 times or more
Want extra protection for some another reason	Never	1 time	2 times	3 times	4 times or more
Other reason not listed	Never	1 time	2 times	3 times	4 times or more

Appendix 3. ENCePP checklist for study protocols

Not applicable

Appendix 4. ANNEX 4. Additional information

Not applicable

## 1. AMENDMENTS FROM PREVIOUS VERSION(S)

None.

## 2. INTRODUCTION

Hemophilia A and B are chronic inherited bleedings disorders caused by an X-chromosome linked deficiency in coagulation factors. Although the incidence of hemophilia is relatively low, it imposes a high level of burden to sufferers, caregivers, and society. As hemophilia requires lifetime treatment it is associated with substantial costs, particularly direct costs. Factor replacement therapy, used for both prophylaxis and on-demand therapy, is the mainstay of hemophilia treatment and has been estimated to cost more than \$250,000 per adult in the United States. Depending on the disease severity and treatment regimen, factor replacement products accounts for 45% to 93% of the total medical costs for hemophilia.

Newer, longer acting treatments for hemophilia have recently been approved by the FDA. Alprolix is a longer-acting treatment than traditional treatments that was approved by the FDA in March, 2014 for hemophilia B. And similarly, for hemophilia A, Eloctate was approved in 2014 and Adynovate in 2015. These newer, longer-acting drugs require less frequent administrations than Pfizer's BeneFIX (for hemophilia B) and Xyntha (for hemophilia A). Even a relatively small change in frequency of administration has the potential to translate into 50 or fewer infusions per year and a correspondingly smaller number of units infused per patient. The expected advantages of fewer infusions from longer acting products include greater patient compliance, less disruptions in daily activities and less reliance on others to help with infusions. However; these benefits are only realized if there is indeed fewer infusions associated with the longer-acting products compared with the shorter-acting products. To date, little is known about real world administration patterns for longer-acting treatments in comparison to traditional treatments. Pfizer is seeking to generate evidence which validates the hypothesis they have that Alprolix , Eloctate, and Adynovate are being dosed more often than their labeling indicates, thus potentially costing payors and patients more money compared to traditional treatments, like BeneFIX and Xyntha.

### 2.1. Study Design

This study will be conducted as a prospective observational, cross-sectional epidemiological study in U.S. site-based clinical practice settings. Participating physicians / clinicians at approximately 30 sites will enroll approximately 300 patients for inclusion in the study. Participating patients – or their caregiver in the case of patients under the age of 18 - will be consented to participate. After this consent occurs, the physicians will complete a retrospective chart review on each enrolled patient, entering their findings into a chart review form (CRF) online. Patients will complete a one-time study questionnaire, which should take approximately 20 minutes to complete, by accessing a link online. The patient questionnaire will include self-report questions regarding patient demographics, clinical profile, treatment, and physician-patient relationship, along with several validated scales to assess health-related quality of life. In addition, patients will submit their health insurance claims data to the study team for analysis. All survey questionnaires will be in English. All respondents will be provided remuneration for their participation.

Protocol # B1821056  
Statistical Analysis Plan

## 2.2. Study population

The study will involve approximately 300 patients recruited from approximately 30 participating sites. The table below shows the specific breakdown in sample size for each hemophilia type and treatment cohort.

**Table 1. Study Sample**

	Sample Size	
	Xyntha	Eloctate or Adynovate
Hem A Patients / Caregivers of Hem A Patients	75	75
Total Hem A	150	
	Alprolix	BeneFIX
Hem B Patients / Caregivers of Hem B Patients	75	75
Total Hem B	150	
TOTAL	300	

This study will compare Xyntha vs. Eloctate /Adynovate among hemophilia A patients and Alprolix vs. BeneFIX among hemophilia B patients. For a mean difference comparing two independent means with the anticipated sample sizes (75 vs. 75; 150 total) with  $\alpha=0.05$ , two-sided, 80% power, the expected minimal detectable effect (MDE) would be Cohen's  $d=0.46$ . This study with the anticipated sample size is powered to detect at least a moderate effect size.

The inclusion and exclusion criteria for physicians and patients are specified below.

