8.2. Setting

The study will occur in a site-based clinical practice setting, meaning that patients will be recruited by physicians to participate in the study. Eligible sites will be activated on an ongoing basis and evaluated continuously as necessary to achieve cohort fulfillment. Sites will identify patients according to criteria specified within protocol and patients will further be qualified within the web questionnaire. The Kantar Health research team will closely monitor patient enrollment between sites to ensure equal distribution across the four cohorts is achieved. If needed, additional sites will be contracted and activated to meet total cohort sample size. All physician and patient materials will be completed online via a web-link to a survey provided by Kantar Health.

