8.4. Data sources

This study will be conducted with physicians and patients in an online setting. Prior to participating, patients will be asked to provide their informed consent in order to proceed with the web surveys and provision of their health care insurance claims.

The physicians participating in this research will be asked to reference their patient medical records for each enrolled patient during their portion of the study.

There will be three sources of data for each patient (or caregivers of patients in the case of minor patients):

- Patient responses to a web survey/questionnaire
- Physician responses to a CRF concerning the same patient
- Patients' medical and pharmacy claims data obtained directly by the patient from their healthcare insurer and provided to Kantar Health via a secure, dedicated email address.

No personal identifiable information will be captured in either the CRF or patient questionnaire. However, the medical claims component of the patient data may include confidential information. Therefore, we will ensure that all personal identifiable data are removed from the claims when the claims are received by Kantar Health. Once Kantar Health study staff receives claims via the dedicated email address, all identifying information (name, date of birth, or other individual identifiers) are redacted using mark-up application that puts a black bar over this data. The claims document is then numbered with the patient's anonymous study ID number and saved using the study ID number as the document name. The document is also password protected so that the redacting masks cannot be removed by other individuals. All patient data will be reported in aggregate form and participants will only be identified by a random unique ID for reference. Kantar Health will not link any study data to personal information of any patient or physician participant.

It is anticipated that claims data received will vary in type and degree of insurance data across different insurers. As such, the planned process is to extract some of the common variables as seen within sample claims such as date of service, carrier, provider type, service description, cost, and any procedural or diagnosis codes if present. The data will be entered and validated by Kantar Health. Final variable list and data format will be discussed with Pfizer prior to data entry.

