### Physician/Clinician Participants Inclusion Criteria

Participating sites must undergo a contracting procedure and agree to follow the study protocol as well as all terms of the study contract. Participating sites will be led by a physician / clinician (eg, nurse, nurse practitioner, physician assistant, etc.) who will serve as that site's PI/sub-PI. The participating PI/sub-PI must meet all the following inclusion criteria to participate in the study:

- Must be a healthcare provider with at least 60% of time spent in direct patient care
- Board-certified or eligible with a Specialty in Hematology or Hematology-Oncology (if hematologist-oncologist, at least 10% practice is dedicated to treatment of hemophilia)
- Currently manages at least 10 hemophilia A and/or B patients
- Must not be on the FDA debarment list

Protocol # B1821056  
Statistical Analysis Plan

Patient Participants Inclusion Criteria

Participants must meet all of the following inclusion criteria to be eligible for inclusion in the study:

- Willing and able to provide informed consent
- Diagnosed with hemophilia A or B
- Current disease severity is either moderately severe or severe with a clotting factor level of  $\leq 5\%$
- If suffering from hemophilia A, must be currently taking Xyntha (or another standard half-life treatment), Adynovate or Eloctate for at least six months.
  - If currently taking Adynovate or Eloctate, must have been switched from a standard half-life treatment and had been on that prior treatment for at least six months.
- If suffering from hemophilia B, must be currently taking BeneFIX or Alprolix for at least six months.
  - If currently taking Alprolix, must have switched from BeneFIX and had been on that prior treatment for at least six months.
- Infuse at least 3 times per month

In the event of a caregiver responding on behalf of the patient, the above inclusion criteria will be applied for the patient for whom the caregiver is responding.

Patient Participants Exclusion Criteria

Currently enrolled in a clinical trial and/or using investigational product for the treatment of his or her hemophilia

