**2.3. Study Objectives**

The study's primary objective is to compare the dosing and resource utilization patterns of standard half-life treatments vs. extended half-life treatments for the management of hemophilia A and B

- Specifically, the dosing and resource utilization patterns of Xyntha (or other standard half-life treatments) vs. Adynovate or Eloctate (extended half-life) will be assessed for treatment of hemophilia A
- And similarly, the dosing and resource utilization patterns of BeneFIX (standard half-life) vs. Alprolix (extended half-life) will be assessed for treatment of hemophilia B

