### **3. ANALYSIS SETS/ POPULATIONS**

#### **3.1. Full analysis set**

All physicians (N=30) and hemophilia A (N=150) and B (N=150) patients from the study will be available for analysis.

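### The stated d=0.46 is correct for 75 vs 75 independent patients with complete data, but no planned outcome analysis accounts for the roughly 30 sites and the figure is not qualified for the claims loss that the SAP itself expects

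*SAP*

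**What the plan says.** Protocol 8.5 and SAP 2.2 carry the same power statement. It begins "For a mean difference comparing two independent means with the anticipated sample sizes (75 vs. 75; 150 total" and, with two-sided alpha 0.05 and 80% power, arrives at d=0.46. The primary objective (SAP 2.3) is to "compare the dosing and resource utilization patterns of standard half-life treatments vs. extended half-life treatments for the management of hemophilia A and B".

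**Site.** About 300 patients are recruited by clinicians at about 30 sites. Protocol 8.2 says that the research team will "closely monitor patient enrollment between sites to ensure equal distribution across the four cohorts is achieved". It also says: "If needed, additional sites will be contracted and activated to meet total cohort sample size". Balance is thus monitored across cohorts and is not required within a site. SAP 6.1.2 plans chi-square tests and one-way ANOVA. SAP 6.2.3 plans GLMs adjusted for demographic and health history variables found relevant in the bivariate step. The only standard-error correction named (SAP 6.1.3) is for underdispersion. No site term, random effect, GEE or clustered standard error appears.

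**Claims.** SAP 2.1 says "patients will submit their health insurance claims data to the study team for analysis", and SAP 3.1 says "All physicians (N=30) and hemophilia A (N=150) and B (N=150) patients from the study will be available for analysis". SAP 6.2.2, however, warns that claims analyses may be limited because some patients may be unwilling to provide the data. It falls back to descriptive statistics if numbers are very low, and sets no threshold. SAP 5 excludes missing outcomes and reports the subsample, but is worded for CRF and questionnaire items.

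**The concern.** Patients treated at the same site share prescribers, and prescribed infusions per month is a clinician's decision. Correlation within sites is therefore plausible for dosing, which is half of the primary objective. If outcomes are correlated within sites and the analysis ignores it, p-values and confidence intervals are miscalibrated. The direction depends on whether products are concentrated by site or mixed within sites. An underdispersion correction does not address this.

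The other half of the primary objective, resource utilization, rests on claims. Total and hemophilia-specific visits, healthcare costs and Rx costs are six of the ten rows in SAP Table 8. The SAP expects these to be incomplete, yet its only power figure assumes that every patient contributes. A reader would take d=0.46 to cover outcomes for which it is too favourable.

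**Working it through.** **1. The plan's figure.** Inputs from SAP 2.2: n=75 per arm, two-sided alpha 0.05, power 80%.
- Normal approximation: MDE = (1.960 + 0.842) × √(2/75) = 2.802 × 0.1633 = 0.457.
- Noncentral t, 148 df: MDE = 0.460; power at d=0.46 is 79.9%.

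The stated 0.46 is reproduced.

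**2. Site.** The documents give about 30 sites and 150 patients per hemophilia type, hence 150/30 = 5 per type per site if spread evenly. The ICC (ρ) and the product mix are not given; both are assumptions. Suppose each site has a patients on one product and b on the other (a+b=5), with the majority product alternating over sites so that each arm has 75. Then, with total variance 1,

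Var(difference) = 2(1−ρ)/75 + ρ × 30 × (a−b)²/75².

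Dividing by 2/75, the variance under independence, gives the design effect DE = 1 − ρ + ρ(a−b)²/5. The unadjusted test then has type I error of about 2 × [1 − Φ(1.96/√DE)].

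At ρ=0.10:

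| Product mix within site | DE | Type I error |
|---|---|---|
| 5:0 (one product per site) | 1 − 0.10 + 0.10 × 25/5 = 1.40 | 9.8% |
| 4:1 | 1 − 0.10 + 0.10 × 9/5 = 1.08 | 5.9% |
| 3:2 | 1 − 0.10 + 0.10 × 1/5 = 0.92 | 4.1% |

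Simulation of the planned ANOVA (40,000 trials per cell) gave 9.7%, 6.0% and 4.1%.

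**3. Claims.** The return rate is not in the documents; 80%, 60% and 40% are assumed. With n = 75 × return, independent patients and the two-sample t-test as an approximation:

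| Return | n per arm | MDE | Power at d=0.46 |
|---|---|---|---|
| 100% | 75 | 0.46 | 79.9% |
| 80% | 60 | 0.52 | 70.5% |
| 60% | 45 | 0.60 | 57.9% |
| 40% | 30 | 0.74 | 41.8% |

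Number of infusions comes from the CRF and questionnaire, so claims loss does not touch it.

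**4. Is one clustering-adjusted MDE available?** With 30 sites per type and a t reference on 29 df, the MDE is 0.47 with no clustering and 0.70 with one product per site at ICC 0.30. But a site may qualify with 10 hemophilia A and/or B patients, so single-type sites are allowed, and sites may be added. If 15 sites supply a type with 10 patients each (an assumption), the reference has 14 df. The MDE is then 0.49 with no clustering, and with one product per site at ICC 0.30 (DE = 1 + 9 × 0.30 = 3.7) it is 0.95. The result depends on site counts that the documents do not fix.

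**The case against.** The power statement already declares its conditions: independent means and anticipated sample sizes. The study is observational with no single primary endpoint, so no stated decision turns on the exact MDE. That is fair, but it answers only the wording of the MDE. It does not supply a variance method for patients grouped by site.

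A reader might infer that clustering must make the true MDE worse than 0.46, or that p-values will be too small. The documents do not support this. With a 3:2 mix the unadjusted test is conservative; at ICC 0.30 the planned ANOVA reaches 80% power at about d=0.44, so 0.46 would be met. One product at every site is also made less likely by the balance monitoring in Protocol 8.2 and by eligibility: hemophilia A patients on an extended half-life product "must have been switched from a standard half-life treatment and had been on that prior treatment for at least six months", and Alprolix patients must likewise have switched from BeneFIX. Neither rule fixes the mix within a site, so the direction stays open.

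A reader might also infer that the plan ignores missing claims. It does not: SAP 6.2.2 names the problem and has a fallback. What stands is that SAP 3.1 and the MDE were left unchanged beside it.

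Finally, the data source described as "Physician responses to a CRF concerning the same patient" ties a CRF to a patient; it does not show that a site code reaches the analysis file. Site identity is not in the variable lists. A link probably exists, but it has to be confirmed.

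**Conclusion.** The concern holds in limited form. The d=0.46 is correctly computed and is derived for 75 vs 75 independent patients with complete data.

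The omission of site from every planned analysis is a matter of text and depends on no assumed value. Its effect does: at ICC 0.10 with 30 sites of 5 per type, type I error runs from 4.1% to 9.8% across the three mixes examined. The documents do not settle where in that range the study falls, or whether the range applies.

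The claims point is an inconsistency within the SAP. Its direction is known: any loss raises the MDE for the six claims rows, to about 0.52, 0.60 or 0.74 at assumed return of 80%, 60% or 40%. These figures assume independent patients and a t-test approximation to the planned models.

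This should be corrected. It does not invalidate the design, and the four remaining Table 8 rows are unaffected by claims loss.

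**What to change.** (a) Keep the planned GLMs. For the outcome contrasts (Table 8 and the matching unadjusted outcome comparisons, not the covariate-screening tests), use one site-adjusted variance method named before data are seen. An example is delete-one-site jackknife standard errors with a t reference on contributing sites minus 1. In simulation with a negative binomial outcome (assumed mean 8, dispersion 0.5, layouts including unequal sites) its type I error was 4.4% to 6.3%. Confirm that a site code is kept in the analysis file.

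(b) Reword Protocol 8.5 and SAP 2.2 along these lines: *d=0.46 applies to 75 vs 75 independent patients with complete data. It does not allow for site clustering and does not apply to claims outcomes with incomplete return; under assumed return of 80/60/40% the MDE is about 0.52/0.60/0.74 before any site adjustment.* Do not write a clustering MDE range into the text; compute it from the actual number of contributing sites and the product mix for each hemophilia type.

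(c) Correct SAP 3.1: *Claims outcomes are analysed in patients who provided claims; N is reported per arm.*

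The cost is wording in two documents, a change in model code and the site-code check. No new patients are needed. The stated MDE becomes less favourable for claims outcomes, and some intervals may widen.
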